5.2 Pre-dosing evaluations (screening and baseline)

Screening/baseline evaluations are to be conducted within two weeks prior to start of protocol therapy (except CT or PET-CT scanning, which must be within 60 days of informed consent and pulmonary function tests, which must be within 90 days of informed consent). In the event that the patient's condition is deteriorating, laboratory evaluations should be repeated within 48 hours prior to initiation of trial therapy.

- Written informed consent
- Demographic details: age, sex, and self-reported race/ethnicity
- Medical History (as detailed in 5.1.3)
- Concomitant medications (as detailed in 5.1.3)
- Complete physical examination (as detailed in 5.1.4)
- Vital signs: systolic/diastolic blood pressure (BP), pulse rate, respiratory rate, oxygen saturation and temperature
- Pulmonary function tests for thoracic radiotherapy: FEV1 and TLCO (if standard of care tests have not been done in the 90 days prior to consent)
- Height, weight and body surface area (BSA)
- ECOG performance status
- Blood tests:
 - Haematology Hb, white blood cells (WBC) with differential count (neutrophils and lymphocytes) and platelets
 - Biochemistry sodium, potassium, calcium, phosphate, urea, creatinine, total protein, albumin, bilirubin, alkaline phosphatase (alk phos), aspartate aminotransferase (AST) and/or alanine aminotransferase (ALT) and lactate dehydrogenase (LDH)
 - International Normalised Ratio (INR)
- Adverse event assessment (SAEs will be collected from the time a patient consents)
- Pregnancy test (females of childbearing potential only) serum or urine Human Chorionic Gonadotropin (HCG) test to rule out pregnancy at study entry; results must be obtained and reviewed before the first dose of atovaquone is administered or any ionising imaging is performed.
- CT or PET-CT scan of brain/chest/abdomen or chest/abdomen/pelvis (if standard of care scan has not been done in the 60 days prior to consent)
- Radiotherapy planning (refer to detailed guidance in section 12)

Results of standard of care tests or examinations performed before obtaining informed consent and before the start of trial treatment may be used; such tests do not need to be repeated for screening provided that they have been completed within the specified time window.

All screening evaluations must be completed and reviewed to confirm that subjects meet all eligibility criteria. The patient should then be registered on the trial (as detailed in section 4.5) before the first dose of trial treatment.

5.3 Evaluations during the study

5.3.1 Evaluations during week -2 or -3 (day 1 of atovaquone treatment)

On the day the first dose of atovaquone is taken:

- Vital signs: systolic/diastolic blood pressure (BP), pulse rate, respiratory rate and temperature*
- Symptom-directed physical examination, if clinically indicated (as detailed in 5.1)*
- ECOG performance status*
- Blood tests:
 - Haematology (as per screening bloods detailed in 5.2)*
 - \circ $\;$ Biochemistry (as per screening bloods detailed in 5.2)* $\;$
 - Atovaquone pharmacokinetics (PK)
 - Plasma marker of hypoxia (miR-210)
 - Adverse event assessment (SAEs will be collected from the time a patient consents)
- New or changes to existing medications
- FMISO PET-CT scan (as per detailed guidance provided in trial imaging manual)
- Request retrieval of archival diagnostic tumour sample for research purposes
- Dispense atovaquone and advise patient on dietary requirements

* Week -2/-3 assessments need not be repeated if screening tests have been carried out within 2 weeks of atovaquone dispensing visit.

5.3.2 Evaluations during week -1 (following two weeks (+/- 7 days) of atovaquone treatment)

- Vital signs: systolic/diastolic blood pressure (BP), pulse rate, respiratory rate and temperature
- Weight
- Symptom-directed physical examination, if clinically indicated (as detailed in 5.1)
- ECOG performance status
- blood tests:
 - Haematology (as per screening bloods detailed in 5.2)
 - Biochemistry (as per screening bloods detailed in 5.2)
 - Atovaquone pharmacokinetics (PK)
 - Plasma marker of hypoxia (miR-210)
- Adverse events and DLTs since the previous assessment clinician to identify clearly in medical notes any AE that is a DLT according to criteria for this protocol
- New or changes to existing medications
- FMISO PET-CT scan (as per detailed guidance provided in trial imaging manual)
- Review patient compliance with atovaquone dosing
- Dispense additional supply of atovaquone if this will be needed prior to next review (opened bottles may be used for up to 21 days)

The week -1 visit (including FMISO PET-CT scan) should be carried out as close to day 1 of CRT as possible. Ideally on Friday of week -1 with CRT commencing Monday of week 1, but within a maximum of one week prior to commencing CRT. Following completion of the week -1 visit and atovaquone run-in patients will commence standard of care chemoradiotherapy in week 1. During chemoradiotherapy the following evaluations are required:

5.3.3 Evaluations during week 1

- Adverse events and DLTs since the previous assessment
- New or changes to existing medications
- Review patient compliance with atovaquone dosing
- Dispense additional supply of atovaquone if this will be needed prior to next review (opened bottles may be used for up to 21 days)

5.3.4 Evaluations during weeks 2, 3, 4, 5, 6 and 7:

Once per week complete the following assessments:

- Vital signs: systolic/diastolic blood pressure (BP), pulse rate, respiratory rate and temperature
- Weight
- Symptom-directed physical examination, if clinically indicated (as detailed in 5.1)
- ECOG performance status

- Blood tests:
 - Haematology (as per screening bloods detailed in 5.2)
 - Biochemistry (as per screening bloods detailed in 5.2)
- Pregnancy test (weeks 2 and 6 only)
- Adverse events and DLTs since the previous assessment
- New or changes to existing medications
- Review patient compliance with atovaquone dosing
- Dispense additional supply of atovaquone if this will be needed prior to next review (opened bottles may be used for up to 21 days)

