ARCADIAN participants will receive two weeks (+/- 7 days) of treatment with atovaquone prior to commencing CRT. As demonstrated in the ATOM trial, seven days of treatment is sufficient to achieve a reduction in tumour hypoxia. Patients will not have their CRT delayed due to enrolment on the trial, as atovaquone run in will occur while patients are waiting for their standard of care CRT to begin. Atovaquone treatment will then continue concurrently with CRT, for a total duration of 59 days (+/- 7 days).

Cisplatin and vinorelbine

Concurrent CRT is the standard of care for patients with locally advanced NSCLC and good performance status. The CRT regime used is variable across the UK with variation in the type of chemotherapy (e.g. cisplatin and etoposide vs. cisplatin and vinorelbine) and the number of cycles of chemotherapy (two or four). Participants in the ARCADIAN trial will receive two cycles of cisplatin and vinorelbine. This has been selected due to being a widely accepted regimen in the UK, and one that is deliverable at the intended research sites. Vinorelbine has also been chosen in preference to etoposide as atovaquone has been found to increase plasma levels of etoposide and its metabolite when given for PCP prophylaxis to children undergoing treatment for acute lymphoblastic leukaemia.

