To initiate clinical studies investigating whether atovaquone holds significant promise as a hypoxia modifying and thus radiosensitising drug, a window-of-opportunity clinical trial in patients with operable NSCLC – the 'Atovaquone as Tumour HypOxia Modifier' (ATOM) trial was completed in late 2018. The primary endpoint of this study utilised tumour hypoxia imaging to assess the effect of atovaquone treatment at the top licenced dose of 750 mg BD on tumour hypoxia. FMISO PET-CT scans were arranged at baseline and repeated following approximately 14 days of atovaquone treatment and the tumour HV compared. Tumour regions with a tumour-to-blood FMISO uptake ratio (TBR) \geq 1.4 at four hours post-injection were defined as being hypoxic [12]. Of the 15 patients who received atovaquone treatment 11 patients (73%) were classed as responders (defined as \geq 10% reduction in HV) with a median reduction in HV of 28% in these patients. Importantly, as expected from decades of clinical experience using atovaquone, we have observed no toxicity associated with atovaquone use during the ATOM study.

Other compounds such as metformin have also previously been shown to reduce OCR and decrease hypoxia in preclinical models [15]. However, to the best of our knowledge there is currently no clinical trial data confirming these effects. A recent study combining metformin with radical chemoradiotherapy in locally-advanced NSCLC did not show improvement in clinical outcomes [16]. Moreover, our pre-clinical data suggests that atovaquone causes a much greater reduction in tumour hypoxia than metformin does at clinically achievable concentrations [9]. Therefore, atovaquone is currently the best available compound to decrease tumour hypoxia by reducing OCR and this trial is well supported by both pre-clinical and now emerging clinical data.

Combining atovaquone with chemoradiotherapy in NSCLC

Patients will receive two weeks (+/- 7 days) of atovaquone to ensure stable plasma concentrations (achieved after seven days) and then continue treatment throughout CRT. Atovaquone dose will be assigned as per a TiTE-CRM statistical model. The first trial participants will receive 450 mg BD. In the absence of unacceptable toxicity, subsequent patients will be assigned doses up to and including 750 mg BD.

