2 TRIAL DESIGN

This is a phase I, single arm, open-label trial that will utilise a TiTE-CRM to determine the maximum tolerated dose (MTD) of atovaquone in combination with concurrent CRT in NSCLC. Twenty evaluable participants will be recruited at two centres.

Twice daily oral atovaquone will be added to standard concurrent CRT: 66 Gy in 33 fractions, once daily, 5 days a week (Monday-Friday), with cisplatin (80 mg/m² IV on days 1 and 22 of CRT) and vinorelbine (15 mg/m² IV on days 1, 8, 22 and 29 of CRT). Whilst awaiting CRT to start, patients will receive two weeks (+/- 7 days) of oral atovaquone to ensure steady state is reached (after seven days). Wherever possible, two weeks of atovaquone treatment should be administered prior to CRT, but in appreciation of the difficulty often experienced in radiotherapy scheduling and planning as well as treatment targets, a +/- 7 days window is permitted. In addition, hypoxia biomarker data will be collected at baseline (start of atovaquone run-in) and following two weeks (+/- 7 days) of atovaquone. Atovaquone will then be continued without break for the duration of CRT with the CRT schedule remaining constant for all patients at both centres. Assessment for DLTs will be from the first scheduled dose of atovaquone until three months after completion of CRT. CT scans performed at the three-month follow up visit will be reviewed to collect tumour response data.

The trial will start at the lowest dose of atovaquone (450 mg BD). Two participants will receive this dose and escalation will only be considered when we have 12 weeks of safety data (a high-risk period of developing dose-limiting toxicity, DLT) for at least one participant at this dose level, thus preventing inappropriate early dose escalation. Following this initial safety run in, eligible patients will be continuously recruited and the TiTE-CRM will be used to recommend the dose of atovaquone for each patient, as detailed in section 17.3.

Refer to the schedule of events and flow chart for details of the study visits and procedures.

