3 OBJECTIVES AND ENDPOINTS

Primary Objective	Endpoints/ Outcome measures	Time point(s) of evaluation of this end point
 To determine the maximum tolerated dose (MTD), and therefore recommended phase II dose (RPTD), of atovaquone when combined with radical concurrent chemoradiotherapy in patients with non-small cell lung cancer (NSCLC) 	 The dose of atovaquone associated with no more than 48% dose limiting toxicity (DLT) rate (target toxicity level) 	• From week -2/-3 until three months post-completion of CRT
Secondary Objectives		
 To assess the safety and toxicity profile of atovaquone in combination with radical concurrent chemotherapy for NSCLC 	 Adverse events graded per Common Terminology Criteria for Adverse Events (CTCAE) v4.03 	 From screening/baseline until six months post completion of CRT
 To confirm feasibility of measuring hypoxia metagene signature using 3'RNA-Seq in diagnostic NSCLC samples 	 Hypoxia metagene signature from diagnostic tissue using 3'RNA-Seq 	At baseline
 To assess agreement of FMISO PET-CT with plasma miR-210 level and tumour hypoxia gene expression pre-treatment with atovaquone 	 Tumour hypoxic volume determined by FMISO PET-CT Plasma miR-210 level Hypoxia metagene signature from diagnostic tissue using 3'RNA-Seq 	 Week -2/-3 (prior to atovaquone treatment)
 To assess agreement in changes in FMISO PET-CT and plasma miR- 210 level following two weeks (+/- 7 days) of atovaquone 	 Tumour hypoxic volume determined by FMISO PET-CT Plasma miR-210 level 	 Week -2/-3 (prior to atovaquone treatment) Following two weeks (+/- 7 days) of atovaquone treatment
 To assess the tumour response rate at three months following treatment 	 Response to treatment assessed per Response Evaluation Criteria in Solid Tumours (RECIST) V1.1 	Three months post completion of CRT
Exploratory Objectives		
To assess the relationship between plasma atovaquone levels and hypoxia response as measured by FMISO PET- CT and plasma miR-210 level	 Plasma atovaquone concentration Tumour hypoxic volume determined by FMISO PET-CT Plasma miR-210 level 	 Week -2/-3 (prior to atovaquone treatment) Following two weeks (+/- 7 days) of atovaquone treatment

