8.2 Duration of treatment

Atovaquone

Patients will receive two weeks (+/- 7 days) of atovaquone prior to starting CRT, treatment will then continue concurrently with CRT. The last dose of atovaquone will be on the morning of the last fraction of radiotherapy. Total duration of atovaquone treatment will be 59 days (+/- 7 days), unless stopped earlier for toxicity or any other reason.

Cisplatin and vinorelbine

Patients will receive two 21-day cycles of cisplatin/vinorelbine as part of their CRT treatment. Chemotherapy will commence (along with RT) on day 1 in week 1, with the last dose of vinorelbine administered on day 29 (week 5). This will follow two weeks (+/- 7 days) of atovaquone treatment, which will be continued throughout CRT. Altogether, patients will receive chemotherapy on 4 days during the trial (unless omitting doses is clinically indicated). Details of chemotherapy treatment received will be recorded in the eCRF.

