2.2 Objectives

The table below shows the full list of trial objectives and corresponding outcome measures. Objectives in grey will be not analysed by trial statisticians within CSM so are not covered by this SAP.

Primary Objective	Endpoints/ Outcome measures	Time point(s) of evaluation of this end point	Analysis population
To determine the maximum tolerated dose (MTD), and therefore recommended phase II dose (RPTD), of atovaquone when combined with radical concurrent chemoradiotherapy in patients with non-small cell lung cancer (NSCLC)	The dose of atovaquone associated with no more than 48% dose limiting toxicity (DLT) rate (target toxicity level)	From week -2/-3 until three months post-completion of CRT	All patients who have received at least one dose of atovaquone
Secondary Objectives			
To assess the safety and	Adverse events graded per	From screening/baseline until	All patients who have
toxicity profile of atovaquone	Common Terminology	six months post completion of	received at least one dose of
in combination with radical	Criteria for Adverse Events	CRT	atovaquone

concurrent chemotherapy for	(CTCAE) v4.03		
NSCLC	. ,		
To confirm feasibility of measuring hypoxia metagene signature using 3'RNA-Seq in diagnostic NSCLC samples	Hypoxia metagene signature from diagnostic tissue using 3'RNA-Seq	At baseline	
To assess pre-treatment agreement of: 1. FMISO PET-CT with plasma miR-210 level 2. FMISO PET-CT with tumour hypoxia gene expression	 Tumour hypoxic volume determined by FMISO PET-CT Plasma miR-210 level Hypoxia metagene signature from diagnostic tissue using 3'RNA-Seq 	Week -2/-3 (prior to atovaquone treatment)	 All patients with outcome measures from both the baseline FMISO PET-CT scan and the baseline blood sample
To assess agreement in changes in FMISO PET-CT and plasma miR-210 level following two weeks (+/- 7 days) of atovaquone	 Tumour hypoxic volume determined by FMISO PET-CT Plasma miR-210 level 	 Week -2/-3 (prior to atovaquone treatment) Following two weeks (+/- 7 days) of atovaquone treatment 	All patients with outcome measures from FMISO PET-CT scans and blood samples taken at both time points
To assess the tumour response rate at three months following treatment	Response to treatment assessed per Response Evaluation Criteria in Solid Tumours (RECIST) V1.1	Three months post completion of CRT	All patients who commence chemoradiotherapy treatment within the study
Exploratory Objectives			

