3. STUDY METHODS

3.1 Trial Design/framework

Arcadian is a single arm, open-label phase I dose escalation trial using the Time-To-Event Continual Reassessment Method (TiTE-CRM) i.e. a model-based approach to determine the maximum tolerated dose (MTD) of atovaquone in combination with concurrent CRT in patients with NSCLC.

Patients will receive an oral suspension of atovaquone twice daily. The four atovaquone dose levels to be assessed in the TiTE-CRM is as follows:

Dose level	
1	450 mg
2	600 mg
3	675 mg
4	750 mg

Patients will receive atovaquone alone for 1 to 3 weeks during a run-in period followed by 6.5 weeks of concurrent chemoradiotherapy (CRT). The 6.5 weeks of CRT consists of two cycles: Cisplatin ($80 \text{ mg/m}^2 \text{ IV}$)

on days 1 & 22, Vinorelbine (15 mg/m² IV) on days 1, 8, 22 & 29 and thoracic radiotherapy: 66 Gy in 33 fractions, once daily, 5 days a week (Monday-Friday). Therefore, the total treatment duration is expected to be up to 9.5 weeks.

Patients will have follow-up visits at approximately 1, 3 and 6 months after completion of CRT.

The TiTE-CRM will take into account toxicity from the start of the atovaquone run-in period to 12 weeks (84 days) after completion of CRT, so the end of the toxicity assessment period will be approximately the time of the 3 months post-CRT visit.

The figure below shows the study schema

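### The second hypoxia and PK measurement has two unreconciled timing rules, so in a short run-in it can fall before seven days of atovaquone

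*Protocol*

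**What the plan says.** The run-in length is flexible. Protocol 8.2 states: "Patients will receive two weeks (+/- 7 days) of atovaquone prior to starting CRT". SAP 3.1 agrees: "Patients will receive atovaquone alone for 1 to 3 weeks during a run-in period". Its purpose is given in Protocol Section 2: "patients will receive two weeks (+/- 7 days) of oral atovaquone to ensure steady state is reached (after seven days". Protocol 1.4 repeats it: "to ensure stable plasma concentrations (achieved after seven days".

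The second FMISO scan, miR-210 sample and PK sample all belong to the week -1 visit, which carries two timing rules.

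- **Counted from CRT.** The timing paragraph that closes Protocol 5.3.2, and the matching schedule footnote, ask for the visit as late as feasible before CRT: "Ideally on Friday of week -1 with CRT commencing Monday of week 1, but within a maximum of one week prior to commencing CRT".
- **Counted from first dose.** Protocol Section 3 gives the endpoint time point as "Following two weeks (+/- 7 days) of atovaquone treatment". The heading of 5.3.2 uses the same window. SAP 6.1 defines the pre-CRT measurement as week -1, two weeks (+/- 7 days) after atovaquone starts, and before any CRT.

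The schedule of events puts the first-dose visit at Day -21 to -8 and the week -1 visit at Day -7 to -1. For the paired-change objective, SAP 2.2 takes "All patients with outcome measures from FMISO PET-CT scans and blood samples taken at both time points". The PK-hypoxia population is built in the same way. Neither states what happens to a measurement taken before 7 days.

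**The concern.** The same +/- 7 days describes both the length of the run-in and the time of the measurement, but the measurement comes before the run-in ends. A site with a short run-in that follows the Friday preference will measure before the seven days that justify having a run-in. The SAP population, as written, keeps that measurement.

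The second measurement feeds one secondary objective (agreement between change in FMISO and change in miR-210) and the exploratory objective relating plasma atovaquone to hypoxia response. Protocol 1.4 wants the change data for designing later trials, including their sample size. Protocol 1.3 classifies response as a reduction in hypoxic volume of at least 10%. If some patients are measured before steady state, their change values are not comparable with the rest, and time on drug may contribute to any PK-hypoxia pattern. With about 20 patients, a few such points could be visible in a plot, and a reader could not identify them unless days on drug are shown.

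Short run-ins are foreseeable. Protocol 1.2 fits the run-in into the wait for CRT and does not delay CRT for the trial, and Protocol Section 2 grants the window because of radiotherapy scheduling.

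**Working it through.** **Check that a 7-day run-in is allowed.** Total atovaquone duration is run-in plus CRT, with CRT taken as 45 days (SAP 6.1):

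- 7 + 45 = 52
- 14 + 45 = 59
- 21 + 45 = 66

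Protocol 8.2 states 59 days (+/- 7), which is 52 to 66. The figure is reproduced exactly, so run-ins of 7 to 21 days are intended.

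**Days on drug at the visit.** Let R be the run-in in days and v the days from the visit to CRT day 1. Protocol 5.3.2 gives v from 1 to 7, with v = 3 for a Friday visit before a Monday start. Elapsed days since first dose are d = R - v.

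| R | v = 1 | v = 3 (Friday) | v = 7 (limit) | slots with d < 7 |
|---|---|---|---|---|
| 7 | 6 | 4 | 0 | 7 of 7 |
| 8 | 7 | 5 | 1 | 6 of 7 |
| 9 | 8 | 6 | 2 | 5 of 7 |
| 10 | 9 | 7 | 3 | 4 of 7 |
| 13 | 12 | 10 | 6 | 1 of 7 |
| 14 | 13 | 11 | 7 | 0 of 7 |
| 21 | 20 | 18 | 14 | 0 of 7 |

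The Friday slot falls short of 7 days for R = 7, 8 and 9. The one-week limit falls short for every R from 7 to 13. From R = 14 no slot does.

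**Can both rules be met?** Both hold when v is at least 1, at most 7, and R - v is at least 7. The number of compliant days is the smaller of 7 and R - 7:

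- R = 7: none
- R = 8: one (v = 1)
- R = 9: two (v = 1 or 2)
- R = 10: three, the shortest run-in for which Friday complies
- R = 14 or more: all seven

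**Conflict in the minimum run-in.** The schedule's latest first dose, Day -8, means R = 8. Protocol 8.2 and SAP 3.1 allow R = 7. These do not agree.

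**Number affected.** The documents give no distribution of run-in lengths. Purely as an assumption, if 10% to 30% of 20 patients were measured early, that would be 0.10 x 20 = 2 to 0.30 x 20 = 6 patients. The possible range is 0 to 20.

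**Counting convention.** These are elapsed days. Counting the visit day as a day on drug adds one to each entry and moves each threshold by one day.

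**The case against.** The strongest reply is that a first-dose anchor already exists. SAP 6.1 is the outcome definition, and it places the second measurement 7 to 21 days after atovaquone starts; Protocol Section 3 and the 5.3.2 heading agree. On that view an early scan is outside the definition, not permitted by it. This stands. A reader might infer from the CRT-based window that anything from 0 to 20 days on drug is allowed. The documents do not support that, because it applies one rule and ignores the other. Zero days would also put the first-dose visit and the week -1 visit on the same day, which the schedule separates.

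A reader might also infer that the two rules are incompatible in every short run-in. The arithmetic shows otherwise: only an exact 7-day run-in has no compliant day.

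The harm is not established either. Protocol Section 2 prefers a full two weeks where feasible, and at 14 days every slot complies. Protocol 1.2 says "seven days of treatment is sufficient to achieve a reduction in tumour hypoxia". That makes seven days enough, not necessary, so nothing shows that the hypoxia change at 4 to 6 days is small or absent. FMISO, miR-210 and PK come from one visit, so an early visit shifts them together. Exposure already varies with dose level (450 to 750 mg) and with food (up to three-fold, Protocol 8.3). Pooling with ATOM (Protocol 7.7) is planned only where possible. The 7-17 days quoted for ATOM is treatment duration; Protocol 1.4 puts its repeat scan at about 14 days.

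Finally, SAP Appendix 3, the imaging manual and the Sample Handling Manual are separate documents not available here. They may already list days on drug.

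What remains is that the two rules diverge in short run-ins, no text in hand ranks them, and the SAP does not say how an early measurement is handled.

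**Conclusion.** The point holds as an unreconciled conflict between two timing rules, with a gap in the SAP behind it. For run-ins of 7 to 9 days the Protocol's preferred slot gives 4 to 6 days on drug, and at the one-week limit any run-in under 14 days gives fewer than seven. The seven-day mark is the Protocol's own figure for steady state.

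It would go too far to say that the paired objectives will mix measurements from before and after steady state. That depends on how many run-ins are short and when sites book the visit, and the documents give neither.

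The consequence is limited. The affected objectives are secondary and exploratory, SAP 6.2 plans no formal analysis of them, and the DLT/MTD primary does not use these measurements. The conclusion rests on counting elapsed days from first dose and on a Monday CRT start for the Friday slot. It is worth correcting because the correction is cheap.

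**What to change.** **Protocol 5.3.2 and the schedule footnote.** State both anchors together: the week -1 FMISO, miR-210 and PK measurements are taken at least 7 days after first dose wherever possible, within the week before CRT, and before the first CRT treatment. Say how days are counted. Reconcile the 7-day minimum run-in in Protocol 8.2 and SAP 3.1 with the latest first dose of Day -8 in the schedule.

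**SAP 2.2 and 6.1.** Report days from first dose to second scan and to second sample for every patient. Keep all patients in the main descriptive set. Show the paired-change and PK-hypoxia results again without patients measured before 7 days, and mark those patients in the plots.

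**Cost.** Wording only, with no extra scan or sample. SAP 6.1 has the run-in length set before treatment starts, so sites can spot short run-ins when booking. Booking becomes tighter: with a Monday CRT start, an 8-day run-in leaves only Sunday and a 9-day run-in only Saturday or Sunday, so there may be no weekday slot. That is why the rule should read wherever possible, and why the SAP handling is needed even after the Protocol wording is settled. The restricted display will also rest on fewer patients.
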